9. Participants will be given instructions for placing (Home N) or replacing (O3 ABPM) the device if it has to be removed.
10. Participants will be given a phone number to call if they have any questions during the monitoring period.
11. Participants will be given the appropriate (ABPM or HBPM) device log to fill out. This form captures the time a participant goes to sleep and awakens. Additionally, this form can be used to document any time when a participant removes the device and puts it back on.

12. The Actiwatch device will be fitted.
13. The next day, participants will return the device and device log, complete either the post-ABPM or post-HBPM questionnaire based on what device was worn, and be fitted for the opposite device (either O3 ABPM or Home N).
14. At the last visit, participants will return the device and device log and complete either the post-ABPM or post-HBPM questionnaire based on what device was worn.
15. Participant will complete the comparability questionnaire.
16. Participants will complete a non-fasting blood draw and spot urine.
17. Participants will complete an echocardiogram. If the echo lab does not have availability for that day, schedule their echocardiogram within the next two weeks.

Participants will return to the clinic the next day to return their ABPM/HBPM devices and actigraphy (Actiwatch) devices and the participant device log.

Upon returning the devices, the technician will:

1. Review the device log with the participant, verifying times the participant went to sleep, woke up, and took device(s) off. If the participant does not return the device log (or it is blank), be sure to fill it out at the return visit.
2. Download the data from the ABPM, HBPM, and actigraphy devices.
3. Confirm that at least 35 of planned ABPM readings are valid or all three HBPM readings are valid. If this is not the case, the participant will be offered the opportunity to complete a second ABPM or HBPM (along with actigraphy and filling out the participant device log).

For participants who have a complete ABPM (or for those who have the device picked up at their house), the participant device log will be checked for completeness, scanned and saved electronically. Next, we will administer the post-ABPM study visit form.

Upon completion of the physical exam and echocardiogram, we will then process their reimbursement. The participants will receive reimbursement through the mail.

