**If at least 2 readings are NOT obtained, ask the participant to repeat the HBPM period overnight.**

[figure not shown]
**If they say yes**, give the device back to the participant and provide them with instructions again on how to place the device and begin the readings. Also, provide them with a new HBPM device log.

**If they say no**, have the participant complete questions regarding the quality of sleep over the overnight monitoring period and the comfort of the HBPM device using the “POST HBPM QUESTIONNAIRE”.

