## **Better BP Study Visit 3 Checklist**

[ ] COVID-19 Screening [ ] Yes [ ] No

[ ] Symptom Tracker

[ ] Temperature Check

[ ] Device return

[ ] Check the device for complete readings

[ ] HBPM three sleep BP readings [ ] Yes [ ] No

[ ] ABPM ~35 measurements [ ] Yes [ ] No

If No, ask participant to wear the device again to collect all necessary readings or measurements.

If yes, complete the Post Questionnaire (**circle one**: email or in-person)

[ ] Post ABPM Questionnaire

[ ] Post HBPM Questionnaire

[ ] Participant will wear the opposite monitor of Visit 2

[ ] ABPM device

[ ] HBPM device

(Actiwatch device will be remove at visit 4)

[ ] Provide participant with the assigned Device Log Form

[ ] Provide participant with State Anxiety Index for home

(To be completed during night of monitoring)

Completed by \_\_\_\_\_ Date \_\_\_\_\_

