### **AFTER PARTICIPANT ARRIVES**

#### **IF PARTICIPANT COMPLETED THE HBPM DEVICE FIRST**

1. Check a complete recording (i.e. – two sleep BP readings) was obtained.
  - a. Yes      No
2. If yes, complete the post-HBPM questionnaire.
3. If no, ask the participant to repeat the HBPM. Discuss with participant the challenges they encountered with obtaining a complete HBPM.
4. Ask participant what time he/she anticipates going to sleep tonight and waking up tomorrow
  - a. Anticipated time going to sleep: \_\_\_\_\_
  - b. Anticipated time waking up tomorrow: \_\_\_\_\_

5. Initialize ABPM device. Serial number: \_\_\_\_\_

6. Is the participant's non-dominant arm being used for the WatchBP O3 ABPM?      Yes      No

7. Reason for not using the non-dominant arm: \_\_\_\_\_

a. Put "X" next to cuff sizes that will be used

		ABPM (Microlife WatchBP O3)	
Cuff Size	Arm circumference	Dominant arm	Non-dominant arm
Small adult	17-21.9 cm		
Med adult	22-32 cm		
Large adult	32.1-42 cm		
Extra-large	42.1-52 cm		

8. Place cuff on arm

- a. Find brachial artery (perhaps make small mark)
- b. Arrow on cuff over brachial artery, non-latex tubing coming out of cuff top
- c. Bottom of cuff 1" above bend/crease in elbow (if possible)
- d. Equal tension top and bottom of cuff (1 finger easily, 2 fingers snug, top and bottom)
- e. Wrap grey non-latex tubing around back of neck

9. Connect tubing to ABPM device (make sure it will not pull out)
10. Place the O3 device in 'Ambulatory' mode.
11. Explain to participant about importance of remaining still during readings and keeping arm a) relaxed at side or in a "sling-like" position if standing, b) resting on table, arm rest, bed, etc. if sitting/reclining
12. Take one test reading; repeat until obtain a valid reading (max 5 tries)
  - a. If cannot get a valid reading, check for cuff too loose, kink in tubing, tubing not securely connected to ABPM device; if need be, change cuff and/or ABPM device (be sure to record new serial #)
  - b. After getting a good reading, wait 30 secs, then start another reading & immediately cancel it
13. Decide if participant will use shoulder strap (preferred), Microlife belt, own belt, or jacket pocket. Instrument ABPM cover appropriately, insert ABPM in cover, and make sure participant is comfortable with this method of wearing device.
14. Review ABPM device log with participant (and remind them to bring it tomorrow or their next study visit)

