## **Better BP Study Visit 4 Checklist**

[ ] COVID-19 Screening [ ] Yes [ ] No

[ ] Symptom Tracker

[ ] Temperature Check

[ ] Device return

[ ] Check the device for complete readings

[ ] HBPM two sleep BP readings [ ] Yes [ ] No

[ ] ABPM ~35 measurements [ ] Yes [ ] No

[ ] Actiwatch to be remove at this visit

If No, ask participant to wear the device again to collect all necessary readings or measurements.

If yes, complete the following questionnaires

**(circle one:** email or in-person)

[ ] Post ABPM Questionnaire [ ] Trait Anxiety Index

[ ] Post HBPM Questionnaire [ ] Expectations of Outcomes

[ ] Comparability Questionnaire

[ ] Collect non-fasting blood work

[ ] Biospecimens [ ] Urine sample

[ ] Genetic sample

[ ] Echocardiogram

Completed by \_\_\_\_\_

Date \_\_\_\_\_

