### **Frequently Asked Questions about the Home Blood Pressure Device**

**1. What do I do when the device is taking a reading?** The device will be taking three readings while you are sleeping. Make sure before you go to sleep that the tubing is not compressed or obstructed and that you do not sleep on the arm where the cuff is placed. If you feel the cuff inflate and wake up, please remain motionless and do not talk while the monitor is taking a blood pressure reading.

**2. How often will the device take a reading?** After your first test reading, the monitor is going to take a total of three readings, two hours, three hours, and four hours later. For example, if you take your test reading at 10:30PM, the monitor will take one reading at 12:30AM, 1:30AM and 2:30AM.

**3. What should I do if a reading fails?** If a reading fails (usually because of motion, the tube being obstructed, or the cuff not being properly placed), the monitor will NOT attempt to repeat the reading. If you happen to wake up and realize there is an error reading, please adjust the cuff and check that the

**ID** \_\_\_\_\_

cuff is positioned properly two inches above your elbow with the arrow pointing to your brachial artery. If the readings continue to fail, and you are aware of such even after you have remained still and have positioned the cuff properly, please call us at **[contact]** in the morning.

**5. What should I do if the device or cuff gets wet?** Please try to keep the monitor dry. There is no personal danger to you if the monitor or cuff gets wet. The cuff will be uncomfortable if it gets wet, but there will be no permanent damage. If the monitor gets wet, please wipe it down with a towel. If it does not turn on or if it does not take a test reading after the monitor gets wet, please call us at **[contact]**.

ID \_\_\_\_\_

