  - a. **Table 4**, use a 2 x 2 table to determine the agreement hypertension on ABPM and clinic BP (i.e., HYP\_AB\_ATTEND versus HYP\_AB\_UNATTEND); provide the p-value from kappa statistics.
  - b. **Table 5**, use a 2 x 2 table to determine the agreement white coat hypertension on ABPM and clinic BP (i.e., WHIT\_AB\_ATTEND versus WHIT\_AB\_UNATTEND); provide the p-value from kappa statistics.
  - c. **Table 6**, use a 2 x 2 table to determine the agreement masked hypertension on ABPM and clinic BP (i.e., WHIT\_AB\_ATTEND versus WHIT\_AB\_UNATTEND); provide the p-value from kappa statistics.
5. Do the following analysis for **Table 7** for those with complete sleep BP data on ABPM and HBPM:
  - a. For sleep systolic BP, calculate the mean BP (with standard deviation) on ABPM and HBPM.
  - b. Calculate the absolute mean difference with 95% confidence intervals for ABPM vs. HBPM, using a paired T-test.
  - c. Repeat items 5a and 5b for sleep diastolic BP on ABPM and HBPM.
6. **Table 8**. Calculate the number and percentage of side effects and tolerability (**listed in Table 8**) that occurred in ABPM only, HBPM only, both ABPM and HBPM, and occurred for neither ABPM nor HBPM.
7. **Table 9**. Restrict the analysis to those with complete data on attended and unattended BP and complete data on left ventricular mass index .
  - a. Use linear regression to determine the relationship between attended SBP with left ventricular mass index.
  - b. Repeat the analysis for attended DBP, unattended SBP, unattended DBP with left ventricular mass index, separately.

8. **Table 10.** Restrict the analysis to those with complete BP data on unattended and awake ABPM and complete data on left ventricular mass index.
  - a. Use linear regression to determine the relationship between unattended SBP with left ventricular mass index.
  - b. Repeat the analysis for unattended DBP, awake SBP on ABPM, awake DBP on ABPM with left ventricular mass index, separately.
9. **Table 11.** Restrict the analysis to those with complete sleep BP data on ABPM and HBPM and complete data on left ventricular mass index.
  - c. Use linear regression to determine the relationship between sleep SBP on ABPM with left ventricular mass index.
  - d. Repeat the analysis for sleep DBP on ABPM, sleep SBP on HBPM, and sleep DBP on HBPM with left ventricular mass index, separately.

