#### **D.10.2. Data transfer.**

**D.10.2.1. ABPM, sleep HBPM, actigraphy, and Device Logs.** Upon return of the ABPM, HBPM, actigraph, and Device Logs, data will be downloaded to a computer and then backed up to a secure network server. Data will be transferred daily to the PEER Unit at UAB using DatAnywhere, a HIPAA compliant file transfer protocol that we used in our AHA-SFRN study. Monthly reports that track data quality will be generated. If data issues are identified (e.g., frequent ABPM or HBPM reading errors), staff will be re-trained.

**D.10.2.2. Echocardiographic measures.** The echocardiographic studies (with unique study identifiers; i.e. de-identified) will be saved to DVD/CD, and backed up to secure research servers at each site. The studies at UAB will be sent to the Cardiovascular Physiology Research Laboratory at Columbia for analysis.

**D.10.3. Data management and cleaning.** All data cleaning will be managed by a statistician at the UAB PEER Unit supervised by [name]. A uniform data editing algorithm, established by Drs. [name] and [name] and used in prior studies, will be implemented to confirm acceptability of the ABPM data and exclude extreme outliers. Minimal editing is the general rule; less than 0.1% of readings are typically excluded. The awake and sleep periods on ABPM will be defined by the actigraphy recording, complimented by self-report

awake and sleep periods from the Device Log. For sleep BP on HBPM, we will confirm that participants were asleep when the the BP readings were obtained using actigraphy data and the HBPM Device Log.

**D.10.4. Minimum number of BP readings required on ABPM and HBPM.** No consensus exists on the number of readings required to consider an ABPM recording complete. Consistent with our prior studies, we will require 14+ awake BP readings, and 5+ sleep BP readings, and  $\geq 80\%$  of the planned 48 readings (39+ total valid readings). We will require three SBP and DBP readings for a sleep HBPM recording to be complete. We will continue recruitment until 600 participants have complete ABPM and sleep HBPM readings.

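### The documents disagree on whether an HBPM night is complete with two or three sleep readings, and Analysis Plan items 5, 9 and 12 neither choose a rule nor carry over the order adjustment of D.11.5.1

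*Combined protocol and SAP*

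**What the plan says.** **Three readings.** Research plan D.10.4 states "We will require three SBP and DBP readings for a sleep HBPM recording to be complete". In the manual of operations, the Summary asks staff to confirm that "all three HBPM readings are valid" and otherwise to offer a second recording. The paragraph on devices that are picked up or mailed back also says three. The Visit 3 checklist has the line "HBPM three sleep BP readings", with a repeat if the answer is no.

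**Two readings.** The HBPM download procedure says: "If at least 2 readings are NOT obtained, ask the participant to repeat the HBPM period overnight". The Visit 3 data collection form, in the part for participants who wore HBPM first, treats two readings as a complete recording. The Visit 4 checklist has "HBPM two sleep BP readings", and the Visit 4 form agrees with it.

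**Analysis.** Item 5 (Table 7) covers participants "for those with complete sleep BP data on ABPM and HBPM" and compares the two methods with a paired t-test. Items 9 and 12 (Tables 11 and 14) restrict their sets in the same terms. None of the three gives a reading count or refers to D.10.3, D.10.4 or D.10.5. D.11.5.1 compares sleep BP differences by randomisation assignment and adjusts for assignment if they are significant.

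**The concern.** The conflict runs between the research plan and the manual, within the manual, and within a single visit: at Visit 3 the checklist and the data collection form give different counts.

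Two things are at stake. First, the field rule and the analysis rule can pull apart. If staff work to two readings, a participant with two is sent on without being offered another night, and D.10.4 then removes that participant from the analysis. A night that could have been repeated is lost. If the analysis works to two instead, Tables 7, 11 and 14 rest on a rule that the research plan does not contain. The Analysis Plan does not say which of these happened.

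Second, device order matters for this comparison. HBPM-first nights are checked at Visit 3 and ABPM-first nights at Visit 4. If staff followed the checklists alone, the repeat trigger would be fewer than three readings in one sequence and fewer than two in the other. The HBPM minus ABPM difference itself varies by order, so unequal completeness between sequences would move an unadjusted paired mean. D.11.5.1 guards against this, and item 5 omits it.

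Two-reading nights are plausible. The participant instructions say that after a failed reading "the monitor will NOT attempt to repeat the reading". The Visit 2 and Visit 3 forms say instead that the device retries three times. If the forms are right, such nights would be rarer.

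**Working it through.** There is no planned figure to reproduce. The check has three parts.

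**1. The rule in each place**

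| Place | Readings required | Specific to a visit? |
|---|---|---|
| Research plan D.10.4 | 3 | no |
| Manual, Summary (device return) | 3 | no |
| Manual, picked-up or mailed devices | 3 | no |
| Visit 3 checklist | 3 | HBPM-first |
| Manual, HBPM download | 2 | no |
| Visit 3 form | 2 | HBPM-first |
| Visit 4 checklist | 2 | ABPM-first |
| Visit 4 form | 2 | ABPM-first |
| Analysis Plan items 5, 9, 12 | not stated | no |

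**2. Is the D.11.5.1 condition met?**

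Inputs are the sleep means by device order in Table 1 and the confidence intervals in Table 7 (N = 547).

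- HBPM minus ABPM, HBPM-first: 106.9 − 103.4 = 3.5 systolic; 62.9 − 60.1 = 2.8 diastolic.
- HBPM minus ABPM, ABPM-first: 105.7 − 104.7 = 1.0 systolic; 61.8 − 60.4 = 1.4 diastolic.
- Contrast between orders: 2.5 systolic, 1.4 diastolic.
- SD of the paired difference = half-width / 1.96 × √547. Systolic: 0.75 / 1.96 × 23.39 = 8.9. Diastolic: 0.55 / 1.96 × 23.39 = 6.6.
- SE of the contrast with two nearly equal groups = 2 × SD / √547 = 0.77 systolic, 0.56 diastolic.
- t = 2.5 / 0.77 = 3.3 systolic; 1.4 / 0.56 = 2.5 diastolic.

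Rounding of the published limits alone gives 3.1 to 3.5 and 2.3 to 2.7. If the Table 1 means are also taken at their worst rounding, the contrasts fall to 2.3 and 1.2 and t to 2.8 and 1.96. The condition is met for systolic pressure and very probably for diastolic. The Table 1 means are not restricted to the 547, so this is an approximation.

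Each method reads higher when worn first (ABPM 104.7 against 103.4; HBPM 106.9 against 105.7). That looks like a first-night effect and needs no reading rule to explain it.

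**3. How far could the mean move?**

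The documents give no failure rate. Assume independent failure with probability p = 2%, 5% or 10% per reading.

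- Exactly two of three readings: 3p(1 − p)² = 5.8%, 13.5%, 24.3% of first nights.
- All three: (1 − p)³ = 94.1%, 85.7%, 72.9%.
- Fewer than two: 0.1%, 0.7%, 2.8%.

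Suppose the checklists governed repeats, every offered repeat was accepted, and the analysis required three readings. With q = (1 − p)³, HBPM-first participants pass with probability q + (1 − q)q. ABPM-first participants pass with q + P(fewer than two) × q. Expected numbers are:

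| p | HBPM-first, of 301 | ABPM-first, of 302 | Systolic difference | Diastolic difference |
|---|---|---|---|---|
| none lost | 301 | 302 | 2.25 | 2.10 |
| 2% | 300 | 285 | 2.28 | 2.12 |
| 5% | 295 | 261 | 2.33 | 2.14 |
| 10% | 279 | 226 | 2.38 | 2.17 |

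Each difference is the order-specific difference weighted by the numbers retained, for example (3.5 × 279 + 1.0 × 226) / 505 = 2.38. The largest movement is 0.13 mm Hg. If all repeats were declined and one rule applied to both sequences, the expected movement would be nil. An order-adjusted estimate with equal weights stays at (3.5 + 1.0) / 2 = 2.25 whatever the losses, provided they are random within each sequence.

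**The case against.** The strongest reply is that a definition already exists. D.10.4 uses the word complete and sets three readings; the forms' thresholds are field triggers for a repeat, not analysis rules. D.10.3 requires confirmation that the participant was asleep, and D.10.5 averages sleep-period readings, so the bedtime test reading is excluded. On this view only a cross-reference is missing. That stands in part, and it is why three readings should be the primary rule. It does not settle the matter. Item 5 does not refer to D.10.4, the research plan describes a different home device from the one in the manual, and the conflict also exists wholly inside the manual. A two-reading trigger also works against a three-reading analysis rule.

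A second reply is that the effect is trivial. For the mean difference this is fair: Table 7 gives −2.3 (−3.0 to −1.5), and a shift of 0.2 or less would not change its reading. Order adjustment would likewise barely move a balanced estimate.

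Three stronger readings are tempting and not supported:

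- A reader might infer that the repeat rule followed the randomised order. That rests on one line of the Visit 3 checklist. The Visit 3 form and the download procedure say two whatever the order; the Summary and D.10.4 say three whatever the order. Order dependence is possible, not established.
- A reader might infer that two-reading nights were dropped from the HBPM-first sequence only, pulling the mean down. That needs an inclusion rule that differs by sequence, and no section states one.
- A reader might try to recover the rule from the fall in N between Tables 2 and 7. The two sets need different data and need not be nested, and D.10.4 has a separate minimum for ABPM sleep readings. The counts are not informative.

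**Conclusion.** The point holds as a contradiction in the completeness rule, not merely as missing detail. Three readings are required in some places and two in others, and the Analysis Plan uses the word complete without choosing. Separately, item 5 leaves out an order adjustment whose condition the reported means appear to meet (contrast 2.5/1.4 mm Hg, t about 3.3/2.5).

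The likely effect on the mean difference is small, about 0.2 mm Hg or less. Its direction depends on whether repeats were offered and accepted. That size rests on assumed failure rates of 2% to 10%, independent readings and the Table 1 means. The number of two-reading nights is not reported, so the effect on the analysed sets (547, 533 and 505 in Tables 7, 11 and 14) cannot be determined from the documents. The order contrast is not evidence that the reading rule did anything.

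This should be corrected, because it leaves the analysis set of a primary aim undefined and the correction is cheap. It does not overturn Table 7.

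**What to change.** 1. In item 5, and by reference in items 9 and 12, define HBPM sleep BP as the mean of the 2, 3 and 4 h readings, confirmed asleep as in D.10.3. Require all three, as in D.10.4, for every night whatever the device order. State which night counts after a repeat.
2. Add a sensitivity analysis that admits nights with two or more readings.
3. Add the D.11.5.1 adjustment for device order to Table 7.
4. Report by device order how many participants had three, two or fewer readings and how many repeated the night.
5. Align the download procedure, the Visit 3 form, and the Visit 4 checklist and form with D.10.4. Settle whether the home device retries a failed reading.

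The cost is a recount from the stored HBPM exports and reruns of Tables 7, 11 and 14, with no new data and no participant contact. The primary set may shrink. If the current 547 already have three readings each, it will not; otherwise the loss is the number of two-reading nights, which the recount will show and the sensitivity analysis will cover.
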